### 5.2. Objectives

The primary Goal of this project is to identify HCV acute and chronic infections in HIV-uninfected MSM and TGW community and to offer them a low barrier linkage to care in the context of a fast-track circuit, offering a first visit with a specialist and starting hep C treatment in the same day after confirmation. A total of 10-15 unknown HCV infections are expected to be diagnosed during the study and to be treated. Potential risk factors for increased HCV infection rates include recreational drug use, including "chemsex", PrEP use, sex work, and several sexual behaviors. We will analyze which factors entangle an increased infection risk. This will allow us to focus and intensify screening on people with these factors while reducing the costs of continuous HCV screening in people who maintain at high risk.

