#### **Phase 1:**

##### **1A. Assess the prevalence of untreated HCV infection among HIV-negative MSM and TGW.**

During the first year all clients of BCN Checkpoint (6,000-7,000) will be offered a serology test, Abbott rapid HCV test "SD BIOLINE HCV assay". It will take 5 minutes to obtain the test results.

If a positive result is obtained in serology test a Cepheid "Xpert® HCV VL Fingerstick" will be performed to identify HCV Viremic cases. The time to obtain the test result will be 60 min approximately.

In case of positive serology and positive viral load, Chemistry and Microbiology HUGTiP laboratories will be used for genotype study and hematology and chemistry.

In case of positive serology with negative viral load, standard lab serology will be also performed to confirm serology, thrown standard hospital lab circuit. If confirmation, this participant will be considered as previously HCV infection with spontaneous cure, if no treatment has been received previously (See table 1).

All participants diagnosticated with viremic HCV infection will be offered a 6 and 12 month post treatment visit to asses possible reinfections. Cepheid "Xpert® HCV VL Fingerstick" will be used as described before to evaluate reinfections. Theses visits will remain without changes during all phases of this study.

**1B.** Also, during the first year, 1.000 subjects with a previous negative "SD BIOLINE HCV assay" will be offered Cepheid "Xpert® HCV VL Fingerstick" tests to detect acute HCV infection if they fulfil at least one of the following criteriaxiii, xiv, xv, xvi, xvii, xviii, xix, xx, xxi, xxii, xxiii, xxiv:

1. Group sex with ChemSex use during last 3 months.
2. Slammering during last 3 months.
3. Fisting without gloves during last 3 months.
4. Sharing anal play toys without condoms during last 3 months.
5. Sharing sniffing roller for cocaine or other drugs during last 3 months.
6. Partner with active HCV or recently diagnosed with HCV on the last 3 months
7. PrEP use\*
8. Previous HCV Infection,
9. HIV infection recently diagnosticated.

*\*PrEP alone as unique criteria will not be considered condition to perform HCV viral load, if it is the only condition, as in our center PrEP users are screened before starting PrEP and each year with serologic screening. Also, HCV screening is performed in case of founding high liver enzymes levels in periodic blood tests performed in PrEP routine controls.*

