## 9. STATISTICAL ANALYSIS

A descriptive analysis will be conducted for the following variables: number of subjects, sociodemographic characteristics (gender, age, and partner's HCV status), sexual behavioral patterns (number of partners, drug use while having sex), PrEP use, and biological results. Results are presented in terms of incidence rate ratios (IRRs) and 95% confidence intervals (CIs) and their p-values of active HCV infections and presented as cases per 100 person-years. Depending on the type or distribution of each variable, absolute frequencies (N) and percentages (%), interquartile range (Q1- Q3), or standard deviation (SD) will be calculated. This descriptive analysis will be presented calculated for individuals separately to allow investigation of the association between groups. Categorical variables will be evaluated by Chi square test or Fisher's test, while Student's t-test or Wilcoxon test was used for continuous variables. After the first phase we will conduct a univariate analysis with all independent factors (HCV risk factors). The outcome variable will be the number of new cases of HCV and taking into account the population at risk. Factors associated with HCV infections with univariate p-value<0.1 will be entered in Poisson regression, adjusted by age and gender. A

significant level of 5% will be taken into account for all analysis performed. Descriptive statistics of demographic factors, and sexual behavior patterns and biological results will also be carried out for possible reinfections detected during follow up visits. A descriptive analysis of the patient reported outcomes will also be carried out and presented in the final report. All analyses will be carried out by means of the STATA 14.2 (StataCorp LP, College Station, TX USA).

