### **11.5. Expected Outcome**

It is expected that HCV screening has a good acceptance in the community. It is also expected to be easy to implement both the HCV test and HCV viral load as the center is used to this kind of tests.

According to the 4.7% prevalence in the MSM community estimated by the ECDC for 2018, it is expected to find 305 positive cases of seroprevalence of HCV infection, but it is unknown how many of them will be viremic, as HCV has actively been treated with DAAs in Spain. Therefore, it will be difficult to determine the number of acute HCV infection cases to be found if HCV viral load screening is performed. Also, in our cohort this number might be influenced by the fact that the center attends a migrant community with higher rates of HCV as well as more frequent Chemsex users.

All these facts make it difficult to estimate the potential number of acute HCV cases, but we expect to find 10-15 cases of acute infections.

Implementing HCV screening among the MSM community will increase the detection of acute cases and, due to higher infectiousness, we can contribute to increase the reduction of the transmission chain among the MSM community. Creating a model that could be implemented in other community centers like BCN Checkpoint will increase HCV detection and treatment, working in line with the WHO 2030 objectives of HCV eradication.

It is also expected that acute HCV detections and partner notification create more awareness around MSM about the importance of HCV prevention.

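### For the acute outcome, the univariate p<0.1 filter works on 10–15 or fewer expected cases and may drop moderate risk factors

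*Combined protocol and SAP*

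**What the plan says.** Section 9 plans a univariate analysis of all HCV risk factors after Phase 1, using chi-square or Fisher tests for categorical factors. It then states: "Factors associated with HCV infections with univariate p-value<0.1 will be entered in Poisson regression, adjusted by age and gender". No other selection rule appears, and there is no prespecified factor set, shrinkage or provision for sparse events. The outcome is described only as follows: "The outcome variable will be the number of new cases of HCV and taking into account the population at risk".

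The text after Table 1 in section 7.2 calls for associated factors for two outcomes, a positive antibody test and a positive acute test. Both feed the Phase 2 selection criteria and the draft pre-test score.

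Acute cases are sought in section 7.2, 1B. There, 1,000 antibody-negative clients are offered viral load "tests to detect acute HCV infection if they fulfil at least one of the following criteria". Nine criteria are listed, but "PrEP alone as unique criteria will not be considered condition to perform HCV viral load".

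On numbers, section 11.5 says "but we expect to find 10-15 cases of acute infections", without tying the figure to 1B or to a phase. Section 5.2 says "A total of 10-15 unknown HCV infections are expected to be diagnosed during the study and to be treated", which covers acute and chronic infections over both phases. For antibodies, section 11.5 says "it is expected to find 305 positive cases of seroprevalence of HCV infection".

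**The concern.** A p<0.1 filter needs events. About 300 antibody positives are enough, but 10–15 acute cases are not, and because section 5.2 gives the same range for all unknown infections in the whole study, the Phase 1 count from 1B could be below 10.

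Two features of 1B add to the problem. Entry requires at least one criterion, so the comparison group for any one criterion consists of people who have another. If the others raise risk, the univariate contrast shrinks; if the others are null, it does not. In addition, section 9 does not say in whom the acute model is fitted. If clients who were never RNA-tested were counted as non-cases, null criteria would look like risk factors, because meeting a criterion is what leads to testing.

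At stake is the acute part of the pre-test score, whose creation and validation is a secondary objective (section 5.2). About 300 Phase 2 clients receive a viral load because they meet it. An antibody-negative client who does not meet the score is not RNA-tested, so Phase 2 is unlikely to recover a factor wrongly left out.

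**Working it through.** **Inputs from the documents.** Filter p<0.1, taken as two-sided (section 9). Acute cases 10–15 (section 11.5), with 8 and 5 also examined because of section 5.2. The 1B sample is 1,000 clients under the entry rule above. The antibody figure reproduces: 0.047 × 6,500 = 305.5, at the midpoint of 6,000–7,000. The 10–15 acute cases cannot be reproduced, as no inputs are given.

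**Events per candidate parameter.** Nine criteria plus age and gender make 11. 8/11 = 0.7, 10/11 = 0.9, 15/11 = 1.4.

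**One factor alone.** With D cases among 1,000 and prevalence p, exposed cases follow Binomial(D, p·RR/(p·RR + 1 − p)). For p = 0.2 and RR 3 the probability is 0.6/(0.6 + 0.8) = 0.43. Over assumed p of 10–50% and D of 10–15:

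| True RR | Passes, Fisher | Passes, chi-square |
|---|---|---|
| 2 | 0.10–0.38 | 0.21–0.41 |
| 3 | 0.24–0.69 | 0.44–0.69 |

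Events for 80% power are (1.645 + 0.842)²/[p(1 − p)(ln RR)²]. At p = 0.2 this is 6.183/(0.16 × 0.480), or 81, for RR 2, and 6.183/(0.16 × 1.207), or 33, for RR 3, both rounded up. With about 300 antibody positives, RR 2 passes at least 98% of the time.

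**Dilution by the entry rule.** Assume six behaviour or contact criteria at 10% with true RRs 4, 3, 3, 2, 2, 1.5, null previous HCV and recent HIV at 1% each, null PrEP at 25%, and independence. A client without the criterion of interest has no other qualifying criterion with probability 0.9⁵ × 0.99² = 0.579.

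- RR 4: the other criteria multiply mean risk by 1.2 × 1.2 × 1.1 × 1.1 × 1.05 = 1.830. Exposed: 4 × 1.830 = 7.32. Unexposed entrants: (1.830 − 0.579)/(1 − 0.579) = 2.97. Apparent RR = 2.5.
- RR 3: the multiplier is 1.3 × 1.2 × 1.1 × 1.1 × 1.05 = 1.982. Exposed 5.95, unexposed entrants 3.33, apparent RR 1.8.

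At latent correlation 0.4 the apparent 1B values are instead 5.4 and 4.2, because each criterion carries some of the others' effect.

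**Untested clients as non-cases.** Suppose one criterion (RR 4) is real and the criteria are independent. A null behaviour shows 1.3/(1.3 − 0.579) = 1.8. At correlation 0.2 and 0.4 it shows about 2.4 and 3.4.

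**Whole procedure, simulated.** The assumptions are as above, with 300–400 replicates per setting and null age and gender. The plan is the filter followed by Poisson regression; the alternative is Firth logistic regression with all nine criteria, age and gender. AUC is measured in 40,000 unselected clients (Monte Carlo SE at most 0.006), and an empty filter scores 0.5 unless stated.

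| Latent correlation | 0 | 0.2 | 0.4 |
|---|---|---|---|
| 12.5 cases: RR 3 passes, Fisher | 21–24% | 48% | 79–81% |
| RR 3 passes, chi-square | 27–32% | 52–54% | 82–83% |
| RR 2 passes, Fisher | 9–10% | 26–28% | 52–56% |
| No factor kept | 21% | 5% | <1% |
| AUC, filter v Firth | 0.58 v 0.68 | 0.69 v 0.75 | 0.82 v 0.83 |
| AUC loss if an empty filter falls back on a count | 0.06 | 0.05 | 0.01 |
| AUC, unweighted count of criteria | 0.69 | 0.76 | 0.83 |
| 8 cases: RR 3 passes, Fisher | 17–20% | 31–39% | 61–63% |
| AUC, filter v Firth | 0.56 v 0.66 | 0.66 v 0.73 | 0.79 v 0.82 |

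With only two real criteria (RR 3) the loss is 0.03–0.04, or 0.01–0.02 with the fallback. With one real criterion at RR 4 it is 0.01, or nil with the fallback. With one at RR 8 it is nil at 12.5 cases, and at 8 cases the filter with fallback was up to 0.01 better.

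**Errors in the other direction.** A separate simulation used eight criteria at 20%, five real at RR 3, correlation 0.6 and 15 cases. Only 3% of real factors were dropped, but at least one null criterion passed in 93% of runs.

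**The case against.** The strongest objection is that the harm depends on a step the plan does not describe. Nothing says that factors surviving the filter become score items, and section 7.2 (Phase 2) allows the approach to change with first-year results. This stands: the loss is conditional, and the missing score rule and analysis population should be settled together with the filter.

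Second, scoring an empty filter as AUC 0.5 exaggerates the contrast, since Phase 2 needs some score. That is fair. The fallback row is the better guide, and it still shows 0.06 and 0.05 at correlation 0 and 0.2.

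Third, the 10% prevalence and the null PrEP, previous-HCV and recent-HIV effects are assumptions. With 20% prevalence, and with varied prevalences and real effects for those three, joint Firth still gained about 0.06–0.08 / 0.03–0.05 / under 0.01 over the filter with fallback, and nothing with one dominant criterion. The direction therefore holds, but the size depends on correlation.

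Fourth, an unweighted count does as well as Firth in the mixed setting. This stands, and is why the count belongs in the analysis as comparator. It is not always enough: with one RR 8 criterion it gave 0.61–0.65 against 0.67.

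Finally, nothing in the plan says that untested clients will be counted as negative. That is true, but nothing rules it out either.

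**Conclusion.** The concern holds for the acute outcome only. The one selection rule in section 9 has roughly one event per candidate parameter there, and in much of the plausible range it would drop a factor with RR 2 or 3 more often than keep it. When several criteria carry moderate risk and are weakly correlated, the cost to the score is about 0.05–0.06 in AUC even with a sensible fallback. It is about 0.01 at correlation 0.4, and small or nil when one criterion dominates. All these figures rest on assumed prevalences, effects and correlations that the documents do not give. Because the acute score is a secondary objective and the gain is conditional, this is an improvement worth considering rather than a flaw that undermines the study.

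**What to change.** For the acute outcome, replace the univariate filter with a prespecified candidate set: the 1B criteria plus the age and gender already planned, merging or dropping criteria too rare to estimate. Enter them jointly in a Firth-penalised or ridge model fitted only among antibody-negative clients RNA-tested under 1B, and state that untested clients are not counted as non-cases. Model the antibody outcome separately among all antibody-tested clients. Report bootstrap optimism-corrected performance of the acute score beside a simple count of criteria, and write down how coefficients become score items. Keep the univariate results as description.

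The cost is SAP wording, some programming and a somewhat longer score, with no new data or visits. Penalisation does not create information: the small case count will still limit precision.

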## 6. INFORMATION SOURCE AND FIELD

Source documents are the patient's medical records.

Study data will be collected through integrated forms in Salus (QSOFT, Software Salus 2017) that is software to compile user's information used in sites participating in this study. It is allocated in a Secure Server according to Personal Data protection Laws.

During the screening visit, the investigator will provide the participant the informed consent and will let the necessary time to read and understand the study procedures. If the participant agrees to participate in the study, he will sign the consent. One copy of the signed IC will be facilitate to the participant.

A demographics and a sexual behavior questionnaire will be requested to be completed by the study participants at the screening visit (See Appendix 2). Additionally, at the end of each study visit, PROMs questionnaire to evaluate satisfaction will be carried out (See appendix 3)(*In this study and adaptation of SUCE questionnaire will be performedxi*).

Additionally, and in case to be necessary it will be asked to the participant information related to previous HCV infections or in case of a diagnostic to follow treatment received and results of blood test performed on other public health units of Catalonia.

The study visits will be performed in the clinical installations of BCN CheckPoint or BCN PrEP·Point, allocated in Barcelona [name] respectively.

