### 7.2. *Study Schedule of Assessments*

This project will be performed in the BCN Checkpoint and BCN Prep-Point , which is a community center for sexual health care and detection of HIV and other STIs for MSM and TGW since 2006.

The services offered by both centers are focused on prevention through early/acute detection of HIV plus fast access to treatment, promotion of biomedical approaches, as well as the promotion of a healthy sexuality among the MSM community.

The center also has experience in systematic detection of asymptomatic STIs and their treatment to prevent their dissemination among the community and the general population. Fast linkage to care has been established in collaboration with "Fundació Lluita contra la Sida" and with the "Hospital Universitari Germans Trias i Pujol", wherein during 2019 a total of 7.581 persons were attended.

This study will have two different phases: phase 1 (first year) and phase 2 (second year).

All the participants should answer the "Sexual Behavior and demographics" questionnaire (Appendix 2), before any blood study extraction during phase 1 and phase 2.

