**Table 1. Study Chronogram Phase 1**

	SCREENING	6 months Post Treatment visit*	12 months Post Treatment visit*
Informed consent	X		
Selection Criteria	X		
SD BIOLINE HCV assay	X		
Cepheid "Xpert® HCV VL Fingerstick"	a X	a X	a X
Xpert® HCV Viral Load	b X		
Routine Serology	c X		
genotype study/Hematology and biochemical analysis	d X		
Sexual behavior & demographics questionnaire	X		
PROMS questionnaire	X	X	X

- a) The participants that obtain a positive result from the SD Bioline HCV assay test will be confirmed with Cepheid "Xpert® HCV VL Fingerstick" to identify HCV viremic cases. Also first 1000 participants with a negative result from the SD Bioline HCV assay test that fulfills criteria mentioned on 1B point, will be confirmed with Cepheid "Xpert® HCV VL Fingerstick" to identify acute HCV infections. \*During V6MPTV and V12MPTM the fingerstick will be offered to all the participants with HCV infection detected during the screening visit.
- b) Acute infections with negative antibodies will be also tested with (Cepheid "Xpert® HCV Viral Load) to confirm viremic cases.
- c) In case of positive serology with negative viral load, standard lab serology will be performed to confirm serology, through standard hospital lab circuit.
- d) For the confirmed HCV Viremic cases, it will be analyzed the following parameters: blood count, Serum Creatinine, AST, ALT, GGT, alkaline phosphatases, direct and indirect Bilirubin, prothrombin time and the genotype study will be performed.

*\* Visits after 6 months and 12 months are optional and only are applicable for those patients that had been diagnosed and treated for HCV infection during the screening visit.*

After one year, a statistical analysis (interim analysis at 6 months\*) of the results will be made to determine associated factors for positive antibody test as well as for positive acute HCV test to set selection criteria for phase 2 of the study. A Draft of HCV pre-test Score will be developed with this first-year analysis and implemented during second phase.

\*Interim analysis will be used to evaluate data collection, correct incidences and to set up data analysis system. This will facilitate the results evaluation at the end of Phase 1 and it will allow to create the pre-test score to start the study Phase 2.

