### **11.4. Risks and potential limitations**

As this project will be included in an ongoing project of community screening, recruitment is not expected to be a problem, however intensification of campaigns for promotion of HCV testing will be considered in case of lack of interest in our actual users.

Questions related to risk factors such as number of sexual contacts, drug use, etc. will be asked by the counselor and could produce an underestimation of these risk factors. However, we have been working with this kind of questionnaires for the last 15 years and users have never expressed any problem due to a peer-to-peer service, which allows a safe environment for the clients. All our staff and volunteers are previously selected and adequately trained.

Users with positive results could refuse to attend the medical specialist in the Hospital Germans Trias due to the distance. In this case derivation to other Hospital could be considered. However, treatment will last only 8-12 weeks and usually require no subsequent follow-up. So, in our opinion the interference of this problem in this study would be extremely limited, other Hospitals on the city are working in Test and Treat HCV strategy and referral has been done in the past; also, we will ask for follow up with the participant through telephone calls.

The Partner notification potential Contacts will be performed in our center in collaboration with the Public Health agency to offer testing to positive case contacts. However, in the MSM community this can sometimes be difficult or even not possible because users don't keep in contact with the most part of their sexual partners. From our center we are going to facilitate to get a test in all suspicious cases of contact to other cases.

Our team has been trained during years in the use of rapid tests, including HIV ELISA, PCR, and Syphilis rapid tests. In this cases HCV viral load could be performed at the same time, but also HCV serology could be sent to the lab, as BCN Checkpoint disposes of nurses and doctors at all opening hours (from 8.00 to 20.00 hours) to perform common blood test through standard venipuncture.

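### Section 9 plans to describe sexual behaviour for reinfections found after treatment, but the only scheduled behaviour questionnaire is at screening, before treatment

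*Combined protocol and SAP*

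**What the plan says.** **The analysis.** Section 9 plans descriptive statistics of demographic factors, "sexual behavior patterns and biological results will also be carried out for possible reinfections detected during follow up visits". It does not say which time point the behaviour data should describe, or where they come from.

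**The questionnaire.** Section 6 states: "A demographics and a sexual behavior questionnaire will be requested to be completed by the study participants at the screening visit". The next sentence treats the satisfaction form differently: "at the end of each study visit, PROMs questionnaire to evaluate satisfaction will be carried out". Tables 1 and 2 show the same contrast. The row "Sexual behavior & demographics questionnaire" has a mark under screening and empty cells at 6 and 12 months, while the PROMs row below it is marked at all three visits.

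**A looser statement.** Section 7.2 says that all participants should answer the questionnaire "before any blood study extraction during phase 1 and phase 2".

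**The follow-up visits.** Under Phase 1A, people diagnosed with viraemic infection "will be offered a 6 and 12 month post treatment visit to asses possible reinfections", using the fingerstick viral load. The footnote to Table 1 makes these visits optional, and they "only are applicable for those patients that had been diagnosed and treated for HCV infection during the screening visit". Section 11.4 adds that "treatment will last only 8-12 weeks and usually require no subsequent follow-up".

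**The concern.** A reinfection, as this plan looks for it, arises after the infection found at screening has been treated. The behaviour that matters for it is behaviour after treatment. The only scheduled form is completed before treatment starts, so the description promised in section 9 would rest on answers from an earlier period.

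Those answers are a poor stand-in for later behaviour. Section 10.1 says that participants receive information on transmission and protection at the visit, and a diagnosis may itself change what people do. A table headed as the behaviour of reinfected participants could therefore be read as the exposure behind the reinfection, when it shows the profile recorded before the earlier infection was treated.

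Reinfection in the first year after treatment is a secondary objective and endpoint. The Rationale names reinfection in a small group with very high-risk practices as the challenge to overcome. With few events expected, relevant exposure data on each one are worth having, and they are hard to recover later.

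**Working it through.** The plan gives no figure for this point, so there is none to reproduce. The check is a comparison of the sections, then the timing, then the scale.

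**1. When behaviour is recorded**

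| Place | Screening | 6 months post treatment | 12 months post treatment |
|---|---|---|---|
| Section 6, behaviour form | yes | not mentioned | not mentioned |
| Table 1, behaviour row | X | empty | empty |
| Table 2, behaviour row | X | empty | empty |
| Section 6 and both tables, PROMs | X | X | X |
| Section 7.2, behaviour form | before any blood draw in phases 1 and 2 | unclear | unclear |
| Section 9, behaviour described for reinfections | - | needed | needed |

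The PROMs row carries all its marks in both tables and section 6 draws the same contrast in prose, so the empty cells are unlikely to come from a broken table.

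**2. Gap between the form and the follow-up visits**

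Inputs:
- Treatment starts on the screening day (the fast-track circuit of sections 5.1 and 5.2). Any delay widens the gap.
- Treatment lasts 8-12 weeks (section 11.4).
- Visits fall 6 and 12 months after treatment (section 7.2).
- One month = 30.44 days.

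Formula: gap = treatment duration + time from end of treatment to the visit.

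- 8 weeks = 56 days = 1.8 months; 12 weeks = 84 days = 2.8 months.
- 6-month visit: 1.8 + 6 = 7.8 months (239 days) to 2.8 + 6 = 8.8 months (267 days).
- 12-month visit: 1.8 + 12 = 13.8 months (421 days) to 2.8 + 12 = 14.8 months (449 days).

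A form completed on the screening day looks backwards. Whatever its recall period, it ends before treatment, so the scheduled form contributes nothing on the post-treatment period.

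**3. Scale, for illustration only**

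Section 5.2 expects 10-15 infections to be diagnosed and treated. The Rationale cites reinfection of almost 25% at two years in HIV-coinfected MSM, a different population. At a constant hazard, the one-year risk is 1 - √(1 - 0.25) = 0.134. Expected reinfections in one year are 10 × 0.134 = 1.3 to 15 × 0.134 = 2.0, so about 1-2, and fewer would be seen if some people skip the optional visits. Section 11.5 attaches the same 10-15 to acute cases and leaves the number of viraemic cases open, so the treated group could be larger.

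**The case against.** **Section 7.2 may already cover follow-up.** The post-treatment fingersticks are blood draws, and the Phase 2 text mentions these visits. Read literally, the questionnaire would precede them. This has some force: part of the defect is an inconsistency between section 7.2 and the tables. But both tables leave the cells empty, section 6 names only the screening visit, and section 11.1 runs the post-treatment visits to September 2024, after Phase 2 ends in July 2023. If the literal reading was intended, the tables still need correcting.

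**Section 9 promises only description.** It does not say that the behaviour must be current, or that behaviours linked to reinfection will be identified; the risk-factor objective concerns acute and chronic infection. This stands. Describing the screening profile of people later reinfected is feasible, but section 9 should then say so.

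**Two stronger readings go too far.**
- A reader might infer that the answers cover exactly the three months before screening. That window belongs to the Phase 1B viral load criteria. The questionnaire (Appendix 2) is a separate document, so its recall period is unknown.
- A reader might infer that no reinfection could have any behaviour data from the relevant period. The documents do not establish this. Only known active infection is excluded, so someone treated in Phase 1 might be screened again in Phase 2 and complete a new form. Medical records are also named as source documents. The plan does not say that either route will be used for reinfections, but neither is ruled out.

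**The impact is small.** This also stands. With about 1-2 expected cases, a comparison of reinfected with non-reinfected attenders would tell little, and the plan does not promise one.

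**Conclusion.** The point holds as a mismatch between a planned description and the data scheduled for it. The one scheduled behaviour form precedes the follow-up visits by about 7.8-8.8 and 13.8-14.8 months and cannot record behaviour after treatment. No other behaviour collection is planned at those visits.

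The month figures assume a same-day treatment start and the stated 8-12 week course. The conclusion depends on neither, nor on the recall period of the form; it needs only that the form is completed before treatment.

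A reader might take this as a threat to the study's main results. It is not: the primary endpoints, the pre-test score and the Poisson model do not use these data. The correction is worth making because it is cheap and gives a secondary, descriptive analysis the exposure data it needs.

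**What to change.** - **Tables 1 and 2 and section 6:** mark the existing sexual behaviour questionnaire at the 6- and 12-month post-treatment visits. It should be completed before the viral load result is known, so that the result cannot colour the answers. Set recall to the time since end of treatment or, if later, the last visit attended.
- **Section 7.2:** align the sentence on timing with the tables, stating whether it covers the post-treatment visits.
- **Section 9:** base the reinfection description on these follow-up answers, as description only, without tests between groups.

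If the sponsor prefers not to add the form, section 9 should state that only behaviour reported at screening is described, and that it does not cover the period in which reinfection occurred.

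**Cost:** a few minutes at each optional visit for about 10-15 people, and a minor amendment. Someone who misses the 6-month visit would be asked to recall up to 12 months, which is less reliable but still covers the right period.
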